4.7.4. Vital Signs and Other Physical Findings

Although measured at the site, vital signs are not recorded in the CRF. No summaries of vital signs are planned.

4.7.5. Safety MRIs

The frequency and percentage of participants with significant treatment-emergent MRI findings, especially Amyloid Related Imaging Abnormalities (ARIA) events such as vasogenic edema (ARIA-E) or microhemorrhage (ARIA-H) will be reported. Fisher's exact test will be used for treatment comparisons.

To evaluate white matter changes over time, a shift table will be created from the following categories:

- 0 = No lesions
- 1 = Focal lesions
- 2 = Beginning confluence of lesions
- 3 = Diffuse involvement of entire region

A listing of MRI data will also be presented.

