9.5. Sample Size Determination

Approximately 200 participants will be enrolled and randomized in a 1:1 ratio to the 2 treatment regimens (donanemab and aducanumab). It is expected that approximately 180 participants will complete 6-month florbetapir F18 PET scans (approximately 90 per treatment regimen). It is

further anticipated that approximately 50% of participants randomized will belong to the intermediate tau subpopulation.

This sample size will provide at least 98% power to demonstrate that donanemab is superior to aducanumab in achieving complete amyloid brain plaque clearance individually at 6 months in the overall population and the intermediate tau subpopulation. Power estimates were obtained using specific contrasts for the 6-month time point of treatment by time interaction effect within the framework of generalized linear mixed effect model assuming a logit link.

The assumptions for this power calculation are that 35.7%, 50.1%, and 54.6% of donanemab treated participants reach complete brain amyloid clearance at 6 months, 12 months, and 18 months, respectively. The corresponding complete brain amyloid clearance percentages for aducanumab treated participants are assumed to be 3.0%, 22.8%, and 27.8%, respectively. The simulation for the power calculation and sample size determination was carried out in SAS Enterprise Guide Version 7.15 and all sample size estimates were obtained assuming a 2-sided significance level of 0.05.

10. Supporting Documentation and Operational Considerations

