
 To assess the superiority of donanemab versus aducanumab on complete brain amyloid plaque clearance. 	
Superiority of percentage of participants who reach complete amyloid plaque clearance on florbetapir F18 PET scan on donanemab versus aducanumab at:
 
 12 months, and 18 months.

 To assess the superiority of donanemab versus aducanumab on complete brain 	
Superiority of percentage of participants who reach complete amyloid plaque clearance on

amyloid plaque clearance in the intermediate tau subpopulation.
	
florbetapir F18 PET scan in the intermediate tau subpopulation on donanemab versus aducanumab at:
 
 • 12 months, and • 18 months.

 • To assess the superiority of donanemab versus aducanumab on degree of brain amyloid plaque reduction in the intermediate tau subpopulation. 	
Superiority of mean absolute change from baseline in brain amyloid plaque on florbetapir F18 PET scan in the intermediate tau subpopulation for donanemab vs aducanumab at:
 
 • 6 months • 12 months, and • 18 months.

 • To assess the superiority of donanemab versus aducanumab on degree of brain amyloid plaque reduction. 	
 • Superiority of change from baseline in brain amyloid plaque reduction on florbetapir F18 PET scan for donanemab 6 months vs aducanumab 12 months.

 • To evaluate the safety and tolerability of donanemab vs aducanumab. 	
Characterization of standard safety assessments:
 
 • Spontaneously reported AEs • Clinical laboratory tests • MRI (ARIA and emergent radiological findings) • Serious hypersensitivity reactions • C-SSRS

Coprimary estimands

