4.7.2. Adverse Events

Treatment-emergent adverse events (TEAEs) will be defined as events that first occurred or worsened after the randomization date (Visit 2 date). Should there be insufficient data for AE start date, stop date, and time to make this comparison, the AE will be considered treatment-emergent. The MedDRA lower-level term (LLT) will be used in the treatment-emergent computation. The maximum severity for each lower-level term (LLT) during the baseline period will be used as baseline.

An overview of AEs, including the number and percentage of participants who died, suffered serious adverse events (SAEs), discontinued due to AEs and who suffered TEAEs, will be provided. Comparison between treatments will be performed using Fisher’s Exact Test.

Summaries of AEs by decreasing frequency of PT within SOC will be provided for the following:

- Preexisting conditions
- TEAEs
- TEAEs by maximum severity
- TEAEs occurring in greater than or equal to 2% of participants by PT
- Serious adverse events
- Adverse events reported as reason for study treatment discontinuation

These summaries will include number and percentages of participants with TEAEs. Treatment comparisons will be carried out using Fisher's Exact Test.

Hypersensitivity and Infusion-Related Reactions (IRR) will be summarized and compared between treatment groups using Fisher's Exact test. Hypersensitivity and IRR will be broken out between Potential Immediate (defined as TEAEs occurring on the date of infusions) and Potential Non-Immediate (defined as TEAEs not occurring on the date of infusions but prior to the administration of a subsequent infusion). The following will be used to identify such TEAEs:

- Anaphylactic reaction SMQ (20000021; narrow, algorithm per SMQ guide, and broad)
- Hypersensitivity SMQ (20000214; narrow and broad)
- Angioedema SMQ (20000024; narrow and broad)
- Event maps to Preferred Term (PT) of Infusion related reaction (10051792)

The number and percentage of participants who experienced a TEAE for the following will be analyzed:

- Any narrow or algorithmic term from any one of the 3 SMQs indicated above (that is, combined search across narrow and algorithmic portions of all 3 SMQs)
- Any narrow scope term within each SMQ, separately (that is, narrow SMQ search)
- Any term within each SMQ, separately (that is, broad SMQ search)

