4.10. Changes to Protocol-Planned Analyses

There are no changes to the protocol planned analyses at this time.

5. Sample Size Determination

This sample size will provide at least 98% power to demonstrate that donanemab is superior to aducanumab in achieving complete amyloid brain plaque clearance individually at 6 months in the overall population and the intermediate tau subpopulation. Power estimates were obtained using specific contrasts for the 6-month time point of treatment by time interaction effect within the framework of generalized linear mixed effect model assuming a logit link.

The assumptions for this power calculation are that 35.7%, 50.1%, and 54.6% of donanemab treated participants reach complete brain amyloid clearance at 6 months, 12 months, and 18 months, respectively. The corresponding complete brain amyloid clearance percentages for aducanumab treated participants are assumed to be 3.0%, 22.8%, and 27.8%, respectively. The simulation for the power calculation and sample size determination was carried out in SAS Enterprise Guide Version 7.15 and all sample size estimates were obtained assuming a 2-sided significance level of 0.05.

6. Supporting Documentation

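### The SAP names no between-arm effect measure or interval for ARIA and the main adverse-event comparisons, so a non-significant Fisher test will not show what excess harm remains possible.

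*SAP*

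**What the plan says.** Safety is a comparative secondary objective in SAP 1.1: "To evaluate the safety and tolerability of donanemab vs aducanumab". The endpoint attached to it is a characterisation of standard safety assessments, with no hypothesis or margin.

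For ARIA, SAP 4.7.5 reports frequency and percentage by arm, and Fisher's "exact test will be used for treatment comparisons". SAP 4.7.2 applies Fisher's test to the AE overview (deaths, SAEs, discontinuations due to AEs, TEAEs), to the tabulations by term, and to hypersensitivity and infusion-related reactions. Of the tabulations it says: "These summaries will include number and percentages of participants with TEAEs". Neither section defines a measure of the difference between arms. Protocol 9.3.5 refers to the SAP for detail.

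SAP 4.1 has a general rule that two-sided CIs are shown at the 95% level. It names no safety quantity. By contrast, SAP 4.4 names the odds ratio and its interval for the co-primary endpoints, and SAP 4.5.1.4 judges non-inferiority on amyloid by an upper confidence limit against 5 centiloids.

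**The concern.** This is a head-to-head trial, and readers will look to it for how the two drugs compare on ARIA and serious events. Per-arm percentages let a reader subtract, but they do not show the uncertainty of the difference. A p-value does not supply it either: above 0.05 it cannot separate a difference near zero from a sizeable excess that a small trial could not resolve. The trial was sized on amyloid clearance, so the precision available for safety is simply whatever 100 per arm gives. If no measure is named in advance, the choice between a risk difference, risk ratio, odds ratio or per-arm interval is left until after the data are seen.

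**Working it through.** **Inputs from the documents.**
- Protocol 9.5: "Approximately 200 participants will be enrolled and randomized in a 1:1 ratio", so about 100 per arm. I take all randomised participants as dosed, so the safety set is also 100 per arm (assumption).
- Protocol 9.5: "approximately 180 participants will complete 6-month florbetapir F18 PET scans (approximately 90 per treatment regimen"), and "approximately 50% of participants randomized will belong to the intermediate tau subpopulation". This gives 45 (completers) to 50 (randomised) per arm in the tau subpopulation.
- SAP Section 5: "35.7%, 50.1%, and 54.6% of donanemab treated participants reach complete brain amyloid clearance" at 6, 12 and 18 months. The corresponding aducanumab "treated participants are assumed to be 3.0%, 22.8%, and 27.8%, respectively".
- Two-sided alpha 0.05 (SAP 4.1 and Section 5).

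**Assumed.** ARIA and AE rates are not given, so the comparator rate is varied from 1% to 35%. No relevant excess is defined either, so 5, 10, 15 and 20 points are tried.

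**1. The plan's own power figure.** Power = Φ{[d - 1.96·√(2p̄(1-p̄)/n)] / √([p1(1-p1) + p2(1-p2)]/n)}, with p1 = 0.357, p2 = 0.030, d = 0.327 and p̄ = 0.1935. At n = 45 this is Φ{(0.327 - 1.96 × 0.0833)/0.0758} = Φ(2.16) = 98.5%. At n = 50 it is 99.2%, and at n = 90 above 99.9%. The stated figure of at least 98% is reproduced, although the plan used a mixed-model simulation. It concerns clearance only; no safety power is stated.

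**2. Fisher power at 100 per arm.** For each pair of true rates, sum Bin(x1; 100, p1) × Bin(x2; 100, p2) over all tables whose two-sided Fisher p is at most 0.05 and whose observed difference is in the direction of harm.

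| Comparator rate | +5 points | +10 points | +15 points | +20 points |
|---|---|---|---|---|
| 1% | 31.5% | 84.0% | 98.4% | 99.9% |
| 2% | 26.6% | 76.2% | 96.3% | 99.7% |
| 5% | 19.0% | 58.6% | 88.3% | 98.1% |
| 10% | 13.8% | 44.4% | 76.2% | 93.5% |
| 20% | 9.9% | 31.3% | 60.8% | 84.4% |
| 25% | 9.2% | 28.5% | 56.4% | 80.9% |
| 30% | 8.7% | 26.3% | 53.5% | 79.2% |
| 35% | 8.4% | 25.8% | 53.0% | 78.8% |

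A 5-point excess is missed in most trials at every rate tried. A 10-point excess is missed in most trials from a comparator rate of 10% upward, but found in most at 5% or below. Excesses of 15 points or more are found more often than not throughout.

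**3. What an interval adds.** The Newcombe interval takes Wilson limits (l, u) for each arm. Its lower limit is d - √[(p1-l1)² + (u2-p2)²] and its upper limit is d + √[(u1-p1)² + (p2-l2)²].

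Take 35/100 versus 25/100. The Wilson limits are 0.264 to 0.447 and 0.175 to 0.343.
- Lower: 0.10 - √(0.086² + 0.093²) = -0.027
- Upper: 0.10 + √(0.097² + 0.075²) = +0.223

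| Events per 100 | Fisher p | Difference, 95% CI (points) |
|---|---|---|
| 35 vs 25 | 0.165 | +10.0 (-2.7 to +22.3) |
| 30 vs 20 | 0.141 | +10.0 (-2.0 to +21.7) |
| 8 vs 3 | 0.213 | +5.0 (-1.7 to +12.3) |
| 25 vs 25 | 1.000 | 0.0 (-11.9 to +11.9) |
| 10 vs 10 | 1.000 | 0.0 (-8.7 to +8.7) |

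The last two rows have the same p-value but exclude different amounts of harm.

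**The case against.** The best defence is that the gap is one of wording. SAP 4.1 already promises 95% CIs unless otherwise noted, and SAP 4.7 notes nothing otherwise. Fisher's conditional distribution also supports an interval: for 35 versus 25 events the conditional odds ratio is 1.61 (0.84 to 3.13). The main analyses of the key secondary endpoints in SAP 4.5.1.2 likewise name no interval, so silence in 4.7 does not prove that safety is excluded from the rule. Finally, the counts are all tabulated, and the registry summaries in SAP 4.6.4 give numbers at risk and numbers with events, so anyone can compute an interval.

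Much of this stands, and it rules out saying that the plan provides no bound at all. It does not settle which quantity the interval describes, and a pre-specified comparative result should not depend on the reader's own calculation.

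A reader might also infer three stronger things that the documents do not support:
- **That the trial is underpowered for safety as a design defect.** Safety is characterised descriptively, with no hypothesis or margin to power for, and adding an interval does not change power.
- **That the sponsor plans to read non-significance as similar safety.** No such rule or claim appears in SAP 4.7.
- **That a relevant excess would usually be missed.** That depends on event rates and on a relevant excess, neither of which the documents state. For example, 5% versus 15% is detected 59% of the time and 20% versus 35% 61% of the time.

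**Conclusion.** The point holds as a moderate reporting gap. For ARIA-E, ARIA-H, SAEs, discontinuations due to AEs and hypersensitivity/infusion reactions, the SAP specifies per-arm counts and percentages and a Fisher p-value. It does not name the between-arm quantity whose uncertainty will be shown. With 100 per arm, a non-significant result can leave an excess of more than 20 points unexcluded when events are common (35 versus 25), and about 9 points even when 10 events are seen in each arm.

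The interval widths rest on the counts shown and on 100 dosed per arm. The power figures rest on assumed comparator rates of 1% to 35%. Neither the validity of the efficacy analyses nor the sample size is in question.

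**What to change.** In SAP 4.7.2 and 4.7.5, for ARIA-E, ARIA-H, SAEs, discontinuations due to AEs and the hypersensitivity/infusion-reaction counts:
- Report the donanemab-minus-aducanumab risk difference with a two-sided 95% CI, by one named method (Newcombe or Miettinen-Nurminen).
- Keep the Fisher p-values as supplementary.
- Base comparative safety statements on the interval limits, and say that a non-significant p-value alone is not evidence of similar safety.
- State that the interval governs where it and the p-value disagree. This can happen: 5 versus 0 events per 100 gives p = 0.059 but a Newcombe interval of +0.3 to +11.2 points.

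The cost is SAP wording and one extra column in existing tables. It needs no new data and does not touch alpha or study conduct. The downside is that the report will show visibly wide intervals.

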4.7.6. Immunogenicity

The frequency and percentage of participants with preexisting (baseline) ADA, ADA at any time after baseline, and TE-ADAs to donanemab will be summarized. If no ADAs are detected at baseline, TE-ADAs are defined as those with a titer 2-fold (1 dilution) greater than the MRD of the assay. For samples with ADA detected at baseline, TE-ADA are defined as those with a 4-fold (2 dilutions) increase in titer compared to baseline. For the TE-ADA subjects, the

distribution of maximum titers will be summarized. The frequency of subjects with neutralizing antibodies (subset of the TE-ADA participants) will also be summarized.

4.7.7. Columbia Suicide Severity Rating Scale

Suicidal ideation, suicidal behavior, and self-injurious behavior without suicidal intent occurring during treatment, based on the Columbia-Suicide Severity Rating Scale (C-SSRS), will be summarized by treatment. In particular, for each of the following events, the number and percent of participants with the event will be enumerated by treatment: completed suicide, nonfatal suicide attempt, interrupted attempt, aborted attempt, preparatory acts or behavior, active suicidal ideation with specific plan and intent, active suicidal ideation with some intent to act without specific plan, active suicidal ideation with any methods (no plan) without intent to act, nonspecific active suicidal thoughts, wish to be dead, and self-injurious behavior without suicidal intent. Although not suicide-related, the number and percent of participants with non-suicidal self-injurious behavior occurring during the treatment period will also be summarized by treatment.

In addition, the number and percent of participants who experienced at least one of various composite measures during treatment will be presented and compared. These include suicidal behavior (completed suicide, non-fatal suicidal attempts, interrupted attempts, aborted attempts, and preparatory acts or behavior), suicidal ideation [active suicidal ideation with specific plan and intent, active suicidal ideation with some intent to act without specific plan, active suicidal ideation with any methods (no plan) without intent to act, non-specific active suicidal thoughts, and wish to be dead], and suicidal ideation or behavior.

The number and percent of participants who experienced at least one of various comparative measures during treatment will be presented and compared. These include treatment-emergent suicidal ideation compared to recent history, treatment-emergent serious suicidal ideation compared to recent history, emergence of serious suicidal ideation compared to recent history, improvement in suicidal ideation at endpoint compared to baseline, and emergence of suicidal behavior compared to all prior history.

Specifically, the following outcomes are C-SSRS categories and have binary responses (yes/no). The categories have been re-ordered from the actual scale to facilitate the definitions of the composite and comparative endpoints, and to enable clarity in the presentation of the results.

Category 1 – Wish to be Dead

Category 2 – Non-specific Active Suicidal Thoughts

Category 3 – Active Suicidal Ideation with Any Methods (Not Plan) without Intent to Act

Category 4 – Active Suicidal Ideation with Some Intent to Act, without Specific Plan

Category 5 – Active Suicidal Ideation with Specific Plan and Intent

Category 6 – Preparatory Acts or Behavior

Category 7 – Aborted Attempt

Category 8 – Interrupted Attempt

Category 9 – Actual Attempt (non-fatal)

Category 10 – Completed Suicide

Self-injurious behavior without suicidal intent is also a C-SSRS outcome (although not suicide-related) and has a binary response (yes/no).

Composite endpoints based on the above categories are defined below.

- Suicidal ideation: A “yes” answer at any time during treatment to any one of the five suicidal ideation questions (Categories 1-5) on the C-SSRS.
- Suicidal behavior: A “yes” answer at any time during treatment to any one of the five suicidal behavior questions (Categories 6-10) on the C-SSRS.
- Suicidal ideation or behavior: A “yes” answer at any time during treatment to any one of the ten suicidal ideation and behavior questions (Categories 1-10) on the C-SSRS.

The following outcome is a numerical score derived from the C-SSRS categories. The score is created at each assessment for each participant and is used for determining treatment emergence.

- Suicidal Ideation Score: The maximum suicidal ideation category (1-5 on the C-SSRS) present at the assessment. Assign a score of 0 if no ideation is present.

Comparative endpoints of interest are defined below. “Treatment emergence” is used for outcomes that include events that first emerge or worsen. “Emergence” is used for outcomes that include events that first emerge.

- Treatment-emergent suicidal ideation compared to recent history:
An increase in the maximum suicidal ideation score during treatment (Visits Y1-Y2) from the maximum suicidal ideation category during the screening and lead-in periods (C-SSRS scales taken at Visits X1-X2). Recent history excludes “lifetime” scores from the Baseline C-SSRS scale or Baseline/Screening C-SSRS scale.
- Treatment-emergent serious suicidal ideation compared to recent history: An increase in the maximum suicidal ideation score to 4 or 5 on the C-SSRS during treatment (Visits Y1-Y2) from not having serious suicidal ideation (scores of 0-3) during the screening and lead-in periods (C-SSRS scales taken at Visits X1-X2). Recent history excludes “lifetime” scores from the Baseline C-SSRS scale or Baseline/Screening C-SSRS scale.
- Emergence of serious suicidal ideation compared to recent history:
An increase in the maximum suicidal ideation score to 4 or 5 on the C-SSRS during treatment (Visits Y1-Y2) from no suicidal ideation (scores of 0) during the screening and lead-in periods (C-SSRS scales taken at Visits X1-X2). Recent history excludes “lifetime” scores from the Baseline C-SSRS scale or Baseline/Screening C-SSRS scale.
- Improvement in suicidal ideation at endpoint compared to baseline:
A decrease in suicidal ideation score at endpoint (the last measurement during treatment; Visits Y1-Y2) from the baseline measurement (the measurement taken just prior to treatment; (Visit X2). This analysis should only be performed for a non-lifetime baseline measurement (i.e., having improvement from the worse event over a lifetime is not clinically meaningful). A specific point in time can be used instead of endpoint.
- Emergence of suicidal behavior compared to all prior history:
The occurrence of suicidal behavior (Categories 6-10) during treatment (Visits Y1-Y2) from not having suicidal behavior (Categories 6-10) prior to treatment (Visits X1-X2). Prior to treatment includes “lifetime” and/or “screening” scores from the Baseline C-SSRS scale, Screening C-SSRS scale, or Baseline/Screening C-SSRS scale, and any “Since Last Visit” from the Since Last Visit C-SSRS scales taken prior to treatment.

Participants who discontinued from the study with no postbaseline C-SSRS value will be considered unevaluable for analyses of suicide-related events. Only evaluable participants will be considered in the analyses. Fisher's exact test will be used for treatment comparisons.

4.8. Other Analyses

4.8.1. Treatment Compliance

Because dosing occurs at study visits, participants who attend all visits and successfully receive donanemab or aducanumab infusions are automatically compliant with this treatment. Any infusion at which 75% (approximately 105 mL) or more of the infusion solution is given will be considered a complete infusion.

Summary statistics for treatment compliance will be provided for the total number of complete infusions received, duration of complete infusion, and volume of complete infusion by treatment group. Frequencies and percentages of reasons why infusion was stopped will also be presented.

4.8.2. Concomitant Therapy

Prior medications are defined as those that stop before randomization (the day prior to the first administration of study drug). Concomitant medications are defined as those being taken on or after randomization (the day prior to the first administration of study drug). A summary of concomitant medications will be presented as frequencies and percentages for each treatment group. Fisher's exact test will be used to test for treatment differences between groups. If the start or stop dates of therapies are missing or partial to the degree that determination cannot be made of whether the therapy is prior or concomitant, the therapy will be deemed concomitant. Medications will be coded using the World Health Organization (WHO) drug dictionary.

